#### **10.3.4. Permitted Medications**

Subjects must be on a stable dose of a single antipsychotic medication, dose within the labeled dose-range, for a minimum of 3 weeks or if above the maximum label dose (country specific) for at least 12 weeks prior to the PET scan at the screening visit, and the dose should remain fixed throughout the study. Depot neuroleptic dose must be stable for at least 2 treatment cycles or at least 30 days (whichever is longer) prior to the screening visit.

Subjects who require an increase in dose of their background antipsychotic during the study will be discussed with the Medical Monitor. A down-titration of the background antipsychotic due to tolerability may be allowable, after consultation with the study medical monitor.

Use of non-prescription pain medications (eg, aspirin, acetaminophen) are allowed during all phases of the study provided these medications do not have a propensity for psychotropic effects and do not interfere with the evaluation of study drug. Hydrocortisone 1% cream or ointment for treatment of contact dermatitis from ECG pads is allowed. Female subjects may use oral, patch, or intrauterine device (IUD) hormonal contraceptives, or progestin implant or injection (detailed information on allowed contraceptives provided in [Section 10.5](#)).

### **10.4. Restrictions**

Subjects must abstain from alcohol from clinic admission through the end of the study.

### **10.5. Contraception Requirements**

Female subject of childbearing potential and male subject with female partner of childbearing potential must agree to use a highly effective form of birth control from 30 days prior to administration of the first dose of study drug, during the treatment period, and 60 days after completion or premature discontinuation from the study drug. Male subjects must also refrain from donation of semen/sperm 30 days prior to administration of the first dose of study drug, during the treatment period, and 60 days after completion or premature discontinuation from the study drug. Continued use of a highly effective form of birth control for males and females is recommended for 2 months after study completion or discontinuation from the study.

Methods that can achieve a failure rate of less than 1% per year when consistently and correctly used are considered as highly effective. Such methods are:

- Combined (estrogen and progestogen containing) hormonal contraception associated with inhibition of ovulation (oral, intravaginal, transdermal).
- Progestogen-only hormonal contraception (oral, injectable, implantable) associated with inhibition of ovulation
- Intrauterine device (IUD)
- Intrauterine hormone-releasing system (IUS)
- Bilateral tubal occlusion
- Vasectomized partner (with surgical success confirmed by medical assessment)
- Sexual abstinence if part of the volunteers preferred lifestyle

Hormonal contraceptives have the following timeframe requirements:

- a) Contraceptive implant implanted at least 90 days prior to screening;
- b) Injectable contraception given at least 14 days prior to screening; or
- c) Oral contraception taken as directed for at least 30 days prior to screening.

Female subjects who are of non-childbearing potential are not required to abide by birth control requirements.

Non-childbearing potential is defined as a subject who is surgically sterile (hysterectomy, bilateral salpingectomy or bilateral oophorectomy) or is postmenopausal (defined as at least 12 months of spontaneous amenorrhea) are not required to remain abstinent or use adequate contraception.

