a Subjects who screen fail may be re-screened up to two times, if judged appropriate by the Investigator. Subjects who screen fail due to MRI or PET or fMRI results may not be re-screened. Screening procedures will occur on multiple days. If subject re-screened, an MRI (without any abnormality) obtained at the study's imaging center within 90 days prior to Day -1 check-in is acceptable for eligibility.

b Extension of in-clinic stay during the screening phase to complete screening assessments may be allowed on a case-by-case basis with pre-approval of the Medical Monitor. Subject must be admitted to the clinic by Day -2.

c Dispensation of study drug on Day 1 and Day 8. All study drug will be taken once daily by mouth from Day 1 through Week 2 (Day 14). After 3 days of treatment with 50 mg/day SEP-363856, subjects are required to titrate up to 75 mg/day. Subjects may dose reduce one time to 50 mg/day for tolerability reasons at any time. Subjects who have a dose reduction for tolerability will continue to receive the reduced dose for the remainder of the study. The final dose, on Day 14, should occur approximately 2 to 4 hours prior to the final PET scan.

d The SCID-CT will be used to support the DSM-5 diagnosis and must be administered by a qualified rater with at least 2 years' experience with the population under study.

e Vital signs will include supine and standing measurements of blood pressure and heart rate, respiratory rate, and oral body temperature.

f Subjects must be fasted (no food or drink except water at least 8 hours prior to specified blood tests). Blood samples should be drawn in the morning followed by a snack or meal.

g Blood samples for follicle stimulating hormone (FSH) will be collected if menopause is suspected.

h Any positive urine  $\beta$ -hCG test should be confirmed by a serum  $\beta$ -hCG test. Must be performed prior to PET scan on same day as screening scan and on Day 14 scan.

i Blood samples for determination of SEP-363856 and SEP-363854 concentrations will be collected on Day 1 (approximately 10 minutes prior to dosing), Day 2 (2 – 4 hours postdose), Day 7 (2 – 4 hours postdose), Day 14 (prior to PET scan), and at Follow-up.

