#### **Screening Period (up to 49 days):**

Informed consent will be obtained from each subject before any study procedures are performed. No imaging procedures involving ionizing radiation will be performed within 12 hours of written consent. Screening procedures will occur over multiple days. Subjects must be on a stable dose of a single antipsychotic medication, dose within the labeled dose-range, for a minimum of 3 weeks or if above the maximum label dose (country specific) for at least 12 weeks prior to the PET Scan at the screening visit, and the dose should remain fixed throughout the study. Subjects who meet entry criteria may be in-clinic for up to 7 days during the screening period, at the Investigator's discretion.

During the screening period, those subjects who are outpatient will report to the imaging center for their PET scan at screening (~2 hours duration) and those subjects who are in-clinic will be transferred to the imaging center accompanied by clinic personnel. The PET scan will be performed prior to dosing (Day -44 to Day -2), with administration of F-DOPA occurring at the start of the PET scan session.

The screening MRI must occur prior to the PET scan at screening (Day -44 to Day -2). Prior to the PET scan at screening, a blood sample will be taken to determine antipsychotic plasma concentrations.

Subjects will check into the clinic on Day -2.

Subjects who screen fail may be re-screened up to two times, if judged appropriate by the Investigator. Subjects who screen fail due to MRI or PET or fMRI results may not be re-screened.

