## 8. SELECTION OF SUBJECTS

### 8.1. Subject Inclusion Criteria

To qualify for participation, subjects must meet all of the following inclusion criteria at screening and Day 1 (including all available predose assessments):

1. Subject must give written informed consent and privacy authorization prior to participation in the study.
2. Subject must be willing and able to comply with the study procedures and visit schedule, including required minimum 2-week in-clinic treatment period, and must be able to understand and follow verbal and written instructions.
3. Male or female subject between 18 to 45 years of age (inclusive) at the time of consent.
4. Subject meets Diagnostic and Statistical Manual of Mental Disorders (DSM-5) criteria for a primary diagnosis of schizophrenia as established by clinical interview (using the DSM-5 as a reference and confirmed using the Structured Clinical Interview for DSM-V Clinical Trials Version [SCID-CT]). The duration of the subject's illness whether treated or untreated must be  $\geq$  6 months.
5. Subject must be on a stable dose of a single antipsychotic medication, dosed within the labeled dose-range, for a minimum of 3 weeks prior to the PET scan at the screening visit. Patients taking clozapine are not eligible to participate.
6. Subject must have a Clinical Global Impression-Severity (CGI-S) score  $\geq$  3 (mild or greater).
7. Subject must have a Positive and Negative Syndrome Scale (PANSS) total score  $\geq$  70.
8. Subject's BMI must be at least 18 kg/m^2 but no more than 35 kg/m^2.
9. Female subjects must have a negative serum pregnancy test at screening; as well as a negative urine pregnancy test prior to the PET scan on each day PET scans are performed, as well as prior to the MRI scan.
  - a. Female subject of childbearing potential and male subject with female partner of childbearing potential must agree to use a highly effective form of birth control (refer to [Section 10.5](#)) from at least 30 days prior to administration of the first dose of study drug, during the treatment period, and 60 days after completion or premature discontinuation from the study drug. Male subjects must also refrain from semen/sperm donation 30 days prior to administration of the first dose of study drug, during the treatment period, and 60 days after completion or premature discontinuation from the study drug.  
In the Investigator's judgment, the subject will adhere to this requirement.

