### 11.4. PET/fMRI Assessments

It is important that the participant is examined under the same conditions at baseline and subsequent scan, including scanning at the same time of day where possible (scanning time of day should be  $\pm$  3h from the time of day of the baseline scan where possible), and head motion monitored and minimised. The post-dose scan should be timed to occur so that the start is approximately at the time in which maximum observed plasma concentration ( $C_{max}$ ) occurs. Post dose fMRI scanning will start approximately 2 to 4 hours after dosing.

Prior to entry into the scanner, subjects will complete the site's standard radiography screening questionnaire to ensure they are safe to enter the scanner environment (eg, no history of surgery involving metal implants). Females will undergo urine pregnancy test to exclude pregnancy. Scan date as well as start and stop time will be collected.

Approximately 1 hour before the scan participants will receive 150 mg of carbidopa and 400 mg of entacapone orally. This inhibits the formation of radiolabeled metabolites of F-DOPA that may cross the blood-brain barrier, and boosts the signal to noise ratio. Subjects will have an IV canula placed in the ante-cubital fossa for administration of F-DOPA. Prior to scanning they will be asked to go to the toilet.

Striatal dopamine synthesis capacity (DSC) assessment ( $K_i$ ) using  $^{18}\text{F}$ -DOPA kinetic analysis will be performed.

In addition to fMRI scan sequences, exploratory MRI sequences may be performed during each of the MRI and PET/MR acquisition times and may include (but not limited to) a neuromelanin-sensitive MRI (NM-MRI) sequence and an iron-sensitive MRI sequence (effective transverse relaxation rate [ $R_2^*$ ] or Quantitative Susceptibility Mapping [QSM]). Repeat MRI including exploratory MRI sequences may be performed where it is not possible to obtain complete measures during the PET-MRI scan.

The majority of participants will receive up to 2 PET scans. Participants will only receive 3 PET scans in the event that a scan is not able to be completed or is not suitable for analysis.

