## **11.9. Study Visits and Assessments**

See [Table 2](#) Schedule of Assessments, for a summary of procedures at each study visit.

### 11.9.1. Screening (Day -49 to Day -2): Visit 1

A unique screening number will be assigned to each subject.

Subjects will be evaluated at the Screening Visit to determine their eligibility to enroll in the study. No imaging procedures involving ionizing radiation will be performed within 12 hours of written consent.

Procedures may be completed in any order unless specified otherwise.

The following study-related procedures will be performed at Screening (procedures will occur over multiple days):

- Obtain signed informed consent and privacy authorization from the subject before conducting any other visit procedures.
- Inclusion and exclusion criteria
- Obtain demographic information.
- Prior/concomitant medications
- Medical history
- Psychiatric history/mental status
- SCID-CT
- Physical examination.
- Height and weight; clinical site staff to calculate and record BMI.
- Vital sign measurements.
- Perform ECG.
- Collect blood sample for clinical laboratory evaluation (hematology, chemistry, serum prolactin, glycosylated hemoglobin [HbA1c], Hepatitis B/C, HIV-1/HIV-2, and fasted glucose panel and lipid panel).
- Collect blood samples for serum pregnancy test (serum human chorionic gonadotropin [ $\beta$ -hCG]) for female subjects and serum follicle stimulating hormone (FSH) for female subjects if menopause is suspected.
- Collect blood sample for antipsychotic levels.
- Collect urine sample for urinalysis and urine drug screen (UDS).
- Perform MRI (MRI at screening must occur prior to the PET scan at screening).
- Perform psychiatric assessments in the following order: PANSS, BNSS, C-SSRS, CGI-S.
- Collect adverse events.
- Perform PET/MR Scan including fMRI (Day -44 to Day -2). Approximately 1 hour before the scan participants will receive 150 mg of carbidopa and 400 mg of entacapone orally.

- Female subjects only, collect urine samples for pregnancy test (any positive test must be followed up with a serum  $\beta$ -hCG test). Urine pregnancy test to be performed on the same day as, but prior to, screening PET/MR Scan.

Subjects who screen fail may be re-screened up to two times, if judged appropriate by the Investigator. Subjects who screen fail due to MRI or PET or fMRI results may not be re-screened.

Re-screened subjects will be re-consented and all screening procedures will be repeated except:

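### Contraception is timed from first dose (latest start Day -30), so a baseline 18F-DOPA PET on Day -44 to Day -31 can come first for a woman newly starting a patch, ring, IUD or IUS; a minor gap, cheaply closed

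*Protocol*

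**What the plan says.** **Contraception.** For women of childbearing potential, and for men whose partners could become pregnant, Section 10.5 states that each "must agree to use a highly effective form of birth control from 30 days prior to administration of the first dose of study drug". Inclusion criterion 9a gives the period as "from at least 30 days prior to administration of the first dose of study drug, during the treatment period" and adds: "In the Investigator's judgment, the subject will adhere to this requirement". Neither place mentions the baseline scan or the tracer. For three hormonal methods Section 10.5 also sets a minimum time in place before screening: implant 90 days, injectable 14 days, oral 30 days. It sets none for the other methods it lists.

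**Baseline scan.** The screening-period text of the Synopsis and Section 7.1 says: "The PET scan will be performed prior to dosing (Day -44 to Day -2". Under Section 7.3.2 a scan involves the tracer (up to 3 mSv), up to two low-dose CT scans (up to 0.7 mSv) and single oral doses of 150 mg carbidopa and 400 mg entacapone.

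**Pregnancy testing.** Inclusion criterion 9 reads: "Female subjects must have a negative serum pregnancy test at screening; as well as a negative urine pregnancy test prior to the PET scan". The urine test applies on each PET day, and another is required before the MRI. Section 11.4 repeats it: "Females will undergo urine pregnancy test to exclude pregnancy". Section 11.9.1 fixes the timing at baseline: "Urine pregnancy test to be performed on the same day as, but prior to, screening PET/MR Scan". Table 2, note h, agrees: "Must be performed prior to PET scan on same day as screening scan and on Day 14 scan". Pregnancy is an exclusion (Section 8.2, item 7), and Section 11.9.2.3 requires a predose urine test on Day 1.

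**The concern.** The protocol treats the scan as an exposure that needs pregnancy safeguards, since it requires a test immediately beforehand. The contraception requirement, however, is counted back from a different and later exposure, the first dose of study drug. Because the scan window opens before the latest permitted contraception start, some women could be scanned while pregnancy testing is the only safeguard the text requires.

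Criterion 9a does not close the gap, although eligibility is checked at screening. It is an agreement about a period counted back from first dose, so a woman can satisfy it at screening without yet using a method.

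At stake is possible exposure of an early pregnancy to the tracer, the CT scans and the two premedications. This is a matter of participant safety only.

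**Working it through.** No figure in the plan needs reproducing. The check is calendar arithmetic followed by a review of the listed methods.

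1. **Latest contraception start.** SAP Section 7.1 numbers days before first dose as date minus first-dose date, with no Day 0. Thirty days before Day 1 is Day -30. Criterion 9a says at least 30 days, so Day -30 is the latest compliant start, not the expected one.
2. **Scan window.** Day -44 to Day -2 is 44 − 2 + 1 = 43 calendar days.
3. **Scan days before Day -30.** Day -44 to Day -31 is 44 − 31 + 1 = 14 days; 14/43 = 33% of the window. The other 43 − 14 = 29 days are Day -30 to Day -2.
4. **How far the scan can precede the required start.** From 44 − 30 = 14 days down to 31 − 30 = 1 day.
5. **Which methods leave the gap open.**
   - Implant, injectable and oral: already in place before screening. With screening on Day -49 the latest starts are Day -139 (49 + 90), Day -63 (49 + 14) and Day -79 (49 + 30), all before any scan.
   - Tubal occlusion, vasectomized partner, lifestyle abstinence: standing arrangements.
   - Patch, ring, IUD, IUS: no lead time before screening, so the gap is open for a new starter. Section 10.5 lists the intravaginal route, but Section 10.3.4 does not name a ring.
6. **What still protects her.** A serum test at screening, a urine test before the MRI and a same-day urine test before the PET. If the serum sample is taken on Day -49, it is 49 − 44 = 5 days old at a Day -44 scan and 49 − 31 = 18 days old at a Day -31 scan.
7. **Is Day -30 a threshold?** For a woman starting on Day -30, the contraceptive lead before the scan is 0 days for a scan on Day -30, 1 day for Day -29 and 30 − 2 = 28 days for Day -2. Study drug has 30 days. Lead time rises gradually from nothing, so protection does not change abruptly at Day -30.
8. **Exposure per scan.** Effective dose to the participant is up to 3.0 + 0.7 = 3.7 mSv. The documents give no fetal dose and no test sensitivity.

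**The case against.** The strongest reply is that pregnancy at the scan is handled directly. Contraception matters most under repeated dosing, when conception can occur during exposure. For a single scan the question is whether the woman is pregnant that day, and a mandatory same-day test addresses it. This stands in large part, and it is why the point is minor. What it leaves is that a test detects an existing pregnancy but does not prevent one between the screening test and the scan.

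A second reply is that the proposed change adds little. Section 7.1 bars ionizing imaging only within 12 hours of consent, so a woman could start a patch at consent, be scanned the next day and comply. A conception before screening would be as likely as before. This also stands: the change acts only on the interval between screening and scan. Counting 30 days back from the scan would cover more, but a Day -44 scan would then need a start by Day -74, outside the 49-day screening period.

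A third reply is that the affected group is hypothetical: a woman of childbearing potential, among 22 planned subjects of both sexes, who newly starts one of four methods as late as allowed and is scanned early. The Investigator must also judge that she will adhere. That is correct, and the number may be zero. The consent form and the site's radiography questionnaire, which were not available for this review, may also contain scan-specific instructions.

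A reader might infer that a third of baseline scans are unprotected. The documents do not support this. The 14 of 43 counts permitted days, no distribution of scan dates is given, and testing applies on every scan day. Nor do they support treating scans from Day -30 onward as safe by contrast, because a scan on or just after that day has little or no contraceptive lead time.

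**Conclusion.** The gap in the wording is real and small. For a woman of childbearing potential newly starting a patch, ring, IUD or IUS at the latest permitted date, the baseline PET can precede the required start of contraception by 1 to 14 days. No other provision in the protocol or SAP closes this.

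The conclusion assumes the SAP's day numbering, the full scan window and a start as late as the text allows. Testing carries most of the protection. The remaining risk cannot be quantified, because the documents give no method mix, scan-date distribution, test sensitivity or fetal dose.

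It would be too strong to say that contraception is tied to study drug for all women, since three hormonal methods are tied to screening. It would also be too strong to say that pregnancy at the scan is unguarded. This is an optional improvement in participant safety.

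**What to change.** In Section 8.1, item 9a, and in Section 10.5, require women of childbearing potential to use highly effective contraception from screening (and in any case before the baseline PET) or from 30 days before first dose, whichever is earlier. Keep the same-day pregnancy test unchanged.

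This cuts the permitted scan days that precede required contraception from 14 to 0 and guards against conception between screening and the scan. It does not address a conception before screening, which still relies on testing.

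The cost is one sentence in each of two places and a possible short delay to the baseline scan for a few women. The endpoint, power and analysis are unaffected.

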## **10.6. Dietary Guidelines**

While subjects are confined to the clinic, meals will be provided. Subjects will receive meals according to the study site procedures.

## 11. STUDY ASSESSMENTS

A study schematic is presented in [Figure 1](#). A summary of assessments to be conducted at each visit is presented in [Table 2](#).

### 11.1. Demographics and Baseline Characteristics

Demographics (date of birth, sex, ethnicity, race), prior and current medications, and medical and psychiatric history will be collected.

A medical history will be obtained by the Investigator or qualified designee as listed on the Form FDA 1572. If the subject's historical medical care was provided at another institution or location, documented efforts must be made to obtain these outside records to verify that the subject meets all inclusion and none of the exclusion criteria. This must be accomplished during the screening period. Alcohol and substance abuse history should also be obtained and documented in the subject's study chart. The Medical History will subsequently be coded using the Medical Dictionary for Regulatory Activities (MedDRA).

